Appendix 5 Clinical Laboratory Tests

The protocol-required clinical laboratory assessments are in the following table:

Laboratory Assessments	Parameters			
Hematology	Platelet count		Mean corpuscular volume (MCV)	White Blood Cell Count with Differential: 
 • Neutrophils • Lymphocytes • Monocytes • Eosinophils • Basophils
	Hemoglobin		Mean corpuscular hemoglobin (MCH)	
	Hematocrit			
	White Blood Cell Count			
	Red blood cell count			
Biochemistry	Blood Urea Nitrogen	Potassium	Aspartate aminotransferase	Total Bilirubin
	Creatinine	Sodium	Alanine aminotransferase	Total Protein
	Glucose	Calcium	Alkaline phosphatase	Cholesterol
	Uric acid	Chloride	γ -Glutamyl-transferase	Triglycerides
	C-reactive protein	Inorganic phosphate	Lactate dehydrogenase	Amylase
		Magnesium	Creatine phosphokinase	Lipase
Routine Urinalysis	
 • Specific gravity • pH, glucose, protein, blood (hemoglobin), ketones, bilirubin, urobilinogen, nitrite, leukocyte esterase by dipstick • Microscopic examination (if blood or protein is abnormal with positive dipstick). 
 • Note: In case of a positive result for hemoglobin, leukocyte esterase, protein or nitrite, a flow cytometry count and classification will be performed 			
Coagulation	
 • INR • aPTT 			
Pregnancy Testing	
 • Serum human chorionic gonadotropin pregnancy test at all time points listed in the Schedule of Assessments (Section 1.3) (as needed for a WOCBP) 			
Other Screening Tests	
 • FSH (as needed if a postmenopausal woman only, at Screening only) • Urine drug screen (to include at minimum: amphetamines, methamphetamines, barbiturates, ecstasy, cocaine, opiates, cannabinoids, benzodiazepines, methadone, phencyclidine, oxycodone, and tricyclic antidepressants) (Screening and Day -1) • Serology (human immunodeficiency virus I and II antibodies, hepatitis B surface antigen, hepatitis B core antibody, hepatitis C antibody, QuantiFERON® Test, at Screening only) • SARS-CoV-2 test (Screening and Day -1) • Thyroid stimulating hormone (TSH, at Screening only) • Cotinine test (Screening and Day -1) • Alcohol breath test (Screening and Day -1) • Estimated Glomerular Filtration Rate based on Chronic Kidney Disease Epidemiology Collaboration Creatinine Equation (2009, Screening only) • Cystatin C (if applicable), at Screening only) 
All study-required laboratory assessments will be performed by a central laboratory, (Nuvisan's clinical laboratory).
			

CCI

Unique Identifier for Version	Date of IAP Version	Author	Changes from the Previous Version
Final 1.0	07-Dec-2021	PPD	Initial version.

4**Purpose of the Integrated Analysis Plan**

The purpose of this IAP is to document technical and detailed specifications for the final analysis of data collected for protocol MS200527_0078. Results of the analyses described in this IAP will be included in the CSR. Additionally, the planned analyses identified in this IAP may be included in regulatory submissions or future manuscripts. Any post-hoc, or unplanned analyses performed to provide results for inclusion in the CSR but not identified in this prospective IAP will be clearly identified in the CSR.

The IAP is based upon Section 9 (Statistical considerations) of the study protocol and protocol amendments and is prepared in compliance with ICH E9. It describes analyses planned in the protocol and protocol amendments.

The wording used in this IAP is chosen to best match the respective wording in the study protocol template, the Clinical Study Report (CSR) template, CDISC requirements and special requirements for table layouts. Therefore, the following approach is used:

Generally, the term ‘participant’ will be used instead of ‘subject’ or ‘patient’. However, in tables and listings the term ‘subject’ will be used to match CDISC requirements, except for in-text tables where ‘participant’ will be used to match the CSR and protocol templates. Similarly, the term ‘study intervention’ will be used in this document instead of ‘treatment’ to match protocol and CSR templates, however, tables and listings will use ‘treatment’ for brevity reasons. Exceptions from this rule are commonly used terms like “on-treatment”, “treatment-emergent”, “treatment policy”, “subject-years”, “by-subject”, or names of eCRF pages like “Treatment Termination” page.

5 Objectives and Endpoints

Objectives	Endpoints
Primary	
To investigate the effect of multiple doses of evobrutinib on single doses of digoxin, metformin, and rosuvastatin (Part 1), and sumatriptan (Part 2) PK in healthy participants	
Plasma transporter substrates $AUC_{0-\infty}$ and C_{max}
Secondary	
Nature, occurrence, and severity of TEAEsAbsolute values and changes in safety laboratory testsSingle 12-lead ECGs evaluated by Investigator, andVital signs assessed from time of first dose to end of study participation
To characterize the effect of evobrutinib on digoxin, metformin, and rosuvastatin (Part 1), and sumatriptan (Part 2) secondary PK parameters in healthy participants	
Plasma PK parameters (Part 1 and Part 2): t_{max}, $t_{1/2}$, and $AUC_{0-tlast}$, CL/F, and Vz/FUrine PK parameters (Part 1, metformin only): Ae_{0-36} and CL_R

CCI

CL/F=apparent total body clearance, CL_R=renal clearance, ECG= electrocardiogram, PK=pharmacokinetics, TEAE=treatment-emergent adverse event, Vz/F= apparent volume of distribution.

6 Overview of Planned Analyses

The final, planned analyses identified in the CSP and in this IAP will be performed after the last participant has completed the last visit and after all data queries resolved as well as the database locked.

A data review meeting will be held prior to database lock for the final analysis. In addition, no database can be locked until this IAP has been approved.

7 Changes to the Planned Analyses in the Clinical Study Protocol

There are no changes to the planned analyses in the clinical study protocol.

8 Analysis Sets and Subgroups

8.1 Definition of Analysis Sets

Analysis Set	Description
Screening	All participants, who provided informed consent, regardless of the participant's enrollment and study intervention status in the study.
Safety (SAF)	All participants, who were administered any dose of any study intervention. Analyses will consider participants as treated.
Pharmacokinetic (PK)	
The PK Analysis Set is a subset of the SAF, and the PK population will include all participants:
 
• Who have completed the study without any relevant protocol deviations and factors likely to affect the comparability of PK results.• With adequate study intervention compliance. 
With evaluable PK data, i.e., no missing values for primary endpoints at each PK profile/assessment day (Day 1, Day 10 for Part 1; Day 1 and Day 8 for Part 2).
 
If participants received prohibited concomitant therapy or medicines, as specified in Section 6.8.3 of the protocol, they will be excluded from the PK population.
 
All PK analyses will be based on this analysis set.

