9.3 Analyses Sets

The analysis populations are specified below in [Table 7](#). The final decision to exclude participants from any analysis population will be made during a data review meeting prior to database lock.

Table 7 Analysis Sets

Analysis Set	Description
Screening	All participants, who provided informed consent, regardless of the participant's enrollment and study intervention status in the study.
Safety (SAF)	All participants, who were administered any dose of any study intervention. Analyses will consider participants as treated.
Pharmacokinetic (PK)	
The PK Analysis Set is a subset of the SAF, and the PK population will include all participants:
 
• Who have completed the study without any relevant protocol deviations and factors likely to affect the comparability of PK results.• With adequate study intervention compliance.• With evaluable PK data, i.e., no missing values for primary endpoints at each PK profile/assessment day (Day 1, Day 10 for Part 1; Day 1 and Day 8 for Part 2). 
If participants received prohibited concomitant therapy or medicines, as specified in Section 6.8.3, they will be excluded from the PK population.
 
All PK analyses will be based on this analysis set.

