16.1.3 Statistical Analysis of PK Parameter Data

Part 1

- **Analysis of Primary Endpoints**

A general linear model with a fixed effect for TREATMENT and a random effect for SUBJECT will be applied to log-transformed PK parameters C_{max} and $AUC_{0-\infty}$ based on the PK analysis set to assess the effect of multiple doses of evobrutinib on the PK of the transporter substrates digoxin, metformin, and rosuvastatin. Treatment differences on the log scale of transporter substrates with evobrutinib vs substrates alone (Day 10 versus Day 1) will be estimated for C_{max} and $AUC_{0-\infty}$ together with their 90% CIs.

Point estimates and CIs will be back transformed to the original scale.

- **Analysis of Secondary Endpoints**

[figure not shown]
The same analysis model as described for the primary endpoints will be provided for the secondary endpoint $AUC_{0-t_{last}}$ of transporter substrates.

The same analysis model as described for the primary endpoints will be provided for the secondary endpoint CL_R of metformin only.

Sensitivity Analyses

The same analyses on the primary and secondary endpoints will be repeated including participants
CCI

Part 2

- **Analysis of Primary Endpoints**

A general linear model with a fixed effect for TREATMENT and a random effect for SUBJECT will be applied to log-transformed PK parameters C_{max} and $AUC_{0-\infty}$ based on the PK analysis set to assess the effect of multiple doses of evobrutinib on the PK of the transporter substrate sumatriptan. Treatment differences on the log scale of sumatriptan with evobrutinib vs sumatriptan alone (Day 8 versus Day 1) will be estimated for C_{max} and $AUC_{0-\infty}$ together with their 90% CIs.

Point estimates and CIs will be back transformed to the original scale.

- **Analysis of Secondary Endpoints**

The same analysis model as described for the primary endpoints will be provided for the secondary endpoint $AUC_{0-t_{last}}$ of sumatriptan.

Sensitivity Analyses

The same analyses on the primary and secondary endpoints will be repeated including participants
CCI

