16.1.4 General Specifications for PK Concentration and PK Parameter Data

Predose samples that occur before the first drug administration will be assigned a time of 0 hours, as if the sample had been taken simultaneously with the study intervention administration. Same applies to the pre-dose sample after multiple doses.

Predose or trough samples which have been taken after the subsequent dosing will be reported as a protocol deviation. The resulting concentrations will be included in concentration listings but excluded from descriptive statistics of concentrations and from PK parameter estimation.

Values BLQ will be taken as zero for summary statistics of PK concentration data, PK parameter estimation (e.g. AUC) and for graphical presentations.

Missing concentrations (e.g. no sample, insufficient sample volume for analysis, no result or result not valid) will be reported and used generally as “N.R.”. A participant who withdraws prior to the last planned observation will be included in the analyses up to the time of discontinuation if still included in the PK analysis set.

If samples are collected outside of 10% of the PK sampling time windows defined in the CSP in section 8.4, these will be included in the PK parameter estimation (NCA) but will be excluded from the concentration summary and mean/median concentration plots.

PK concentrations which are erroneous due to a sampling processing or analytical error (as documented in the bioanalytical report) may be excluded from the PK analysis if agreed by the Sponsor. In this case the rationale for exclusion will be provided in the CSR. Any other PK concentrations that appear implausible to the Clinical Pharmacologist/Clinical PK/PD Scientist will not be excluded from the analysis. Any implausible data will be documented in the CSR.

If important protocol deviations occurred likely to affect the PK profile of participants as specified in Section 10.2.1, the impacted concentrations and PK parameters will be excluded from summary statistics and further statistical evaluation.

Any PK concentrations or PK parameters excluded from summary statistics will be included in participants listings and flagged; a reason for exclusion will be detailed in the CSR (e.g. a footnote or a table of exclusions). Any flags should be included in the study specific CDISC data sets.

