The regression analysis should contain data from at least 3 different time points in the terminal phase consistent with the assessment of a straight line on the log-transformed scale. Phoenix WinNonlin “best fit” methodology will be used as standard. If warranted, further adjustment may be made by the pharmacokineticist, after agreement with the Sponsor. The last quantifiable concentration $> LLOQ$ should always be included in the regression analysis, while the concentration at t_{max} and any concentrations BLQ which occur after the last quantifiable data point $> LLOQ$ should not be used.

If $AUC_{extra\%} > 20\%$ and/or the coefficient of correlation (R^2 adj) of λ_z is < 0.8 and/or the observation period over which the regression line is estimated (span ratio) is less than 2-fold the resulting $t_{1/2}$, the rate constants and all derived parameters (e.g. $t_{1/2}$, $AUC_{0-\infty}$, CL/F , etc.) will be listed, flagged and included in the parameter outputs. Should more than 10% of subjects be flagged for AUC_{extra} and/or R^2 adj (for a particular analyte), a sensitivity analysis excluding flagged parameters may be performed after discussion with the Sponsor.

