16.1.6.1 Listings and Tables

The following PK tables will be produced (PK Analysis Set) by part:

- Descriptive statistics of concentrations by analyte, matrix, study intervention (day)
- Descriptive statistics of PK parameters by analyte, matrix, study intervention (day)

The following PK Listings will be produced (Safety Analysis Set) by part:

[figure not shown]
- Individual concentrations, nominal time by participant, analyte, matrix, day and study intervention (day) sorted in chronological order
- Individual PK parameters by participant, analyte, matrix, day and study intervention (day) sorted in chronological order
- PK Sampling date, actual time, nominal time, deviation from time, percentage time deviation by participant, analyte, matrix and study intervention (day) sorted in chronological order
- Start and end time and date of collection interval, urine volume, concentration, excreted amount by participant, analyte, matrix and study intervention (day) sorted in chronological order
- Phoenix WinNonlin NCA Core Output

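### PK evaluability is set per participant, so one non-derivable AUC0-∞ can, read literally, drop other complete PK pairs (low severity, cheap to fix)

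*SAP*

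**What the plan says.** SAP 8.1 defines one PK Analysis Set. Besides completion without relevant deviations, adequate compliance and no prohibited medicines, a participant must be someone "With evaluable PK data, i.e., no missing values for primary endpoints at each PK profile/assessment day" (Days 1 and 10 in Part 1, Days 1 and 8 in Part 2). It adds: "All PK analyses will be based on this analysis set". Protocol 9.3, Table 7, has the same condition: "no missing values for primary endpoints at each PK profile/assessment day". SAP Section 5 names AUC0-∞ and Cmax of the transporter substrates as the primary endpoints.

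SAP 16.1.3 fits one mixed model to each of these for each substrate. For AUC0-tlast in both parts, and for metformin CLR in Part 1, it says: "The same analysis model as described for the primary endpoints will be provided for the secondary endpoint".

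Three other SAP rules bear on the point:

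- **Terminal regression (16.1.5.1).** "The regression analysis should contain data from at least 3 different time points in the terminal phase". An AUC0-∞ that fails the extrapolation, adjusted R² or span criterion is not set to missing; it "will be listed, flagged and included in the parameter outputs".
- **Important deviations (16.1.4).** Exclusion acts on values: "the impacted concentrations and PK parameters will be excluded from summary statistics and further statistical evaluation".
- **Transporter polymorphism (16.1.6).** Exclusion applies only to the substrate concerned.

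Protocol 9.3 leaves the final decision on exclusions to a data review meeting before database lock.

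**The concern.** The condition attaches to the participant and covers all primary endpoints at once. AUC0-∞ is the fragile one, because it needs a usable terminal slope. Cmax and AUC0-tlast do not, and metformin CLR is Ae0-36 divided by AUC0-36, so it does not need AUC0-∞ either.

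On the literal text, one missing AUC0-∞ therefore removes observed, complete Day 1 versus Day 10 (or Day 8) pairs from the models and summaries. In Part 1 this reaches two probes whose data are intact. The removed values would remain visible only in listings: "The following PK Listings will be produced (Safety Analysis Set) by part".

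Protocol 9.1 makes the analysis descriptive, with no hypothesis test, so the interval around each ratio is the main result. What is at stake is an avoidable loss of precision, and an unwritten choice left to the data review meeting.

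**Working it through.** **1. Values that must be present.** Part 1: 3 substrates × 2 primary parameters × 2 days = 12. Part 2: 1 × 2 × 2 = 4.

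**2. Pairs lost when one probe's AUC0-∞ is missing on one day.**

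| | Modelled pairs per participant (SAP 16.1.3) | Unavailable under any rule | Lost only through the set rule |
|---|---|---|---|
| Part 1 | 3 × (Cmax, AUC0-∞, AUC0-tlast) + metformin CLR = 10 | 1 | up to 9 |
| Part 2 | Cmax, AUC0-∞, AUC0-tlast = 3 | 1 | up to 2 |

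The counts are upper limits. If analyte data were lost, more than AUC0-∞ may be missing, and the affected probe's AUC0-tlast pair may not be comparable between days.

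**3. The plan's own figure.** The Protocol synopsis plans a maximum of 20 assigned per part for about 16 evaluable: 16/20 = 80%, an allowance of 4. The CVs and expected precision (Protocol Tables 5 and 6) are blacked out, so the precision basis of 16 cannot be reproduced.

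**4. Effect of one lost pair.** With complete pairs and a random subject effect, the log-scale 90% CI half-width is

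t(0.95, n−1) × s × √(2/n), where s² = ln(1 + CV²).

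In a ratio of two half-widths s and √2 cancel, so no CV is needed. With h(n) = t(0.95, n−1)/√n:

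- h(20) = 1.7291/4.4721 = 0.3866 and h(19) = 1.7341/4.3589 = 0.3978. Ratio 1.029: 2.9% wider.
- h(16) = 1.7531/4 = 0.4383 and h(15) = 1.7613/3.8730 = 0.4548. Ratio 1.038: 3.8% wider.

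Illustration at an assumed CV of 30% and a ratio of 1: 0.834 to 1.200 with 16 pairs, 0.828 to 1.208 with 15. At CV 10% it is 0.940–1.064 against 0.938–1.066; at CV 40%, 0.788–1.270 against 0.781–1.281.

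**5. Expected effect under an assumed rate.** Let p be the chance that a given probe's AUC0-∞ is missing on either day. The documents do not give p. If losses are independent across probes and 20 start Part 1, the participant rule leaves 20(1−p)³ and a per-substrate rule leaves 20(1−p):

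| Assumed p | Participant rule | Per-substrate rule | CI wider by |
|---|---|---|---|
| 0.4% | 19.76 | 19.92 | 0.4% |
| 1% | 19.41 | 19.80 | 1.1% |
| 3% | 18.25 | 19.40 | 3.5% |

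Losses shared between probes, such as a withdrawal, remove all probes under either rule and make the difference smaller.

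**The case against.** **The wording does not say across all substrates.** Other SAP text can be read as expecting incomplete data within the set: parameter summaries report the number of non-missing observations (16.1.2), deviations remove values (16.1.4), and polymorphism removes one substrate (16.1.6). The data review meeting could apply evaluability per analyte. This stands in part. It means that the loss is not certain. But those rules act on values or substrates within the set; none readmits a participant whom the set definition has removed, and the meeting has no instruction to judge by analyte.

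**The trigger is narrow.** Poorly determined AUC0-∞ values are kept. SAP 16.1.5.1 also lets the pharmacokineticist adjust the regression after agreement with the Sponsor, and lets scheduled times stand in for missing actual times. Sampling is dense: 17 postdose samples to 72 hours in Part 1 and 13 to 24 hours in Part 2. This stands, and it is why the severity is low.

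**A common set has a merit.** The same participants stand behind every ratio, and Protocol and SAP agree on the rule. Both are true, so this is an improvement to a consistent rule rather than the repair of a contradiction.

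A reader might infer that the rule threatens the target of about 16 evaluable, or widens the intervals by 10% or more. The documents do not support that: it would take per-probe rates of about 10%, and no rate is given. Nor can one conclude that no analysis restores these participants. The sensitivity-analysis text in SAP 16.1.3 is partly blacked out; the visible text in 16.1.6 links sensitivity analyses to polymorphism exclusions.

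**Conclusion.** The point holds at low severity. The evaluability rule has no substrate or parameter level, and its literal reading discards complete pairs that the planned models could use: up to 9 of 10 per affected participant in Part 1 and 2 of 3 in Part 2.

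The size that needs no rate assumption is 2.9% (19 against 20) or 3.8% (15 against 16) on the log-scale CI half-width for each affected participant. It rests only on complete pairs and the planned model. Expected totals depend on an unknown rate; at 0.4% to 1% per probe they are about 0.4% to 1.1%, and zero if every AUC0-∞ can be derived. No hypothesis test is affected, and no bias is claimed.

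**What to change.** Before database lock:

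1. In SAP 8.1, define evaluability per substrate and per parameter. Each model, including those for AUC0-tlast and metformin CLR, uses the participants who have that parameter on both profile days.
2. Keep the completion, deviation, compliance and prohibited-medicine criteria at participant level.
3. Include an AUC0-tlast pair only if the data review meeting confirms, before lock, that tlast is comparable on the two days. A profile without a usable terminal slope is where truncation is most likely to differ.
4. Show n for each substrate and parameter.
5. Declare the change from Protocol 9.3 in SAP Section 7, which now reports no changes.

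The cost is a short rewording of SAP 8.1, one entry in Section 7, and one check at a meeting already planned. The downside is that n may differ between ratios, so they would no longer all rest on the same participants.

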8.2 Subgroup Definition and Parameterization

Not applicable.

9 General Specifications for Data Analyses

The results of this study will be reported using summary tables, figures, and data listings, as appropriate. All data will be summarized by study intervention and/or scheduled time point, as applicable.

Listings

In the individual participant data listing all individual data will be listed by part as measured. Repeated and unscheduled measurements will be included in the listings. All listings will be sorted by study intervention, subject ID, and nominal time point, as appropriate.

Tables and Descriptive Statistics

All data will be summarized by study intervention and nominal time point, as appropriate. Repeated and unscheduled measurements included in the listings will not be used for statistical analyses or summaries, unless the repeated measurement was performed due to unreliable values/technical reasons, e.g., clotted samples.

Unless otherwise specified, continuous variables will be summarized using descriptive statistics, i.e. the number of participants with non-missing values (n), the number of participants with missing values, (nmiss), mean, standard deviation, median, 25th percentile (Q1) and 75th percentile (Q3), minimum, and maximum. If there are no missing values the number of participants with missing

values should be indicated by a 0. Mean, Median, Q1, Q3, Min, Max will have the same precision as the SDTM data (decimal places). SD will be presented with one decimal place more than the mean.

Qualitative variables will be summarized by frequency counts and percentages. Unless otherwise stated the calculation of proportions will be based on the number of participants of the analysis set of interest that received the respective study intervention for AE and PK tables and for all other evaluations the analysis set of interest [N]. Therefore, counts of missing observations will be included in the denominator and presented as a separate category.

Study day 1 for this study is defined as the start date of study intervention.

Unless otherwise specified, comparisons will be presented for substrates cocktail with evobrutinib vs. substrates cocktail alone of part 1 and sumatriptan with evobrutinib vs. sumatriptan alone of part 2.

The following labels will be used for the study interventions in tables and listings of Part 1, if not stated otherwise:

Cocktail (Day 1):	Single oral dose substrate cocktail on Day 1: digoxin (0.25 mg), metformin (10 mg), rosuvastatin (10 mg)
Evobrutinib (Days 4 to 9):	45 mg Evobrutinib multiple doses twice daily on Days 4 to 9
Evobrutinib+Cocktail (Day 10):	45 mg Evobrutinib multiple oral doses twice daily on Days 4 to 12 plus Cocktail on Day 10

The following labels will be used for the study interventions in tables and listings of Part 2, if not stated otherwise:

Sumatriptan (Day 1):	25 mg Sumatriptan single oral dose on Day 1
Evobrutinib (Days 2 to 7):	45 mg Evobrutinib multiple doses twice daily on Days 2 to 7
Evobrutinib+Sumatriptan (Day 8):	45 mg Evobrutinib multiple doses twice daily on Days 2 to 8 plus Sumatriptan on Day 8

Note: The label "Evobrutinib" is applicable to adverse event (AE) tables and listings only.

All tables, listings and figures will be provided by part.

All statistical analyses will be performed using SAS® Software version 9.2 or higher.

